2.3 Advance care planning outcomes		
Advance directive completion		Medical record
Self-efficacy, readiness for ACP		Patient survey
ACP discussions		Patient survey

Potential Modifiers of ACP Outcomes (Secondary Analysis): To identify aMCI participant characteristics that might influence feasibility and ACP outcomes, we will also examine the relationship between baseline cognitive function or mood symptoms (Table 6) and ACP outcomes. For example, we will examine whether better memory function or better executive functions are associated with advance directive completion. Cognitive, mood, and informant data from Bio-AD will be available for secondary analyses and will be referred to as their ‘baseline’ cognitive data. For participants who are not also participating in Bio-AD, we will a) offer participation in Bio-AD if they agree to participate in the recruitment data base, or b) not collect these baseline measures that are outlined in Table 6 due to the additional time requirements.

Table 6. Cognitive and Mood Measures Collected in [name] Study

	Primary Variable	Description
Cognitive		
Memory	SENAS: Memory Composite	Learning and delayed recall performance on a word list task.
Executive Functions	SENAS: Working Memory Composite	Verbal and visual working memory performance
	NACC Trail Making Test B (Total Time)	Cognitive flexibility and switching performance
Mood		
Depression	Geriatric Depression Scale (Total Score)	30-item questionnaire of current mood
Stress	Perceived Stress Scale (Total Score)	10-item questionnaire of recent perceived stress

We will collect qualitative data on implementation process measures, including interviews with patients and study partners, to understand the ACP-GV intervention from multiple perspectives.

B. Description of Population to be Enrolled:

Population and Setting:

Individuals with amnesic Mild Cognitive Impairment and study partners from UHealth settings: Memory Disorders Clinic, Seniors Clinics.

Aim 1 will recruit 6 older adults (\geq age 60) with aMCI and 6 associated study partners.

Aim 2 will recruit 20 older adults (\geq age 60) with aMCI and 20 associated study partners.

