Inclusion criteria for the diagnosis of aMCI will be based on the National Institute on Aging and Alzheimer's Association workgroup *clinical* criteria for MCI,¹⁷ but will depart from the core clinical criteria in that we will focus specifically on individuals with early memory impairment. The rationale for this decision is that our goal is to enrich our aMCI cohort for likely AD pathology and minimize the likelihood of a non-degenerative primary etiology. Study criteria will thus include the following clinical determinations: a) cognitive complaint that reflects a decline in cognition; b) preservation of independence in functional activities; and c) not meeting criteria for a dementia. Additionally, objective neuropsychological impairment in one or more domains, including memory, will be based on either 1) inclusion as aMCI in [name] study which uses comprehensive criteria by Jak;¹⁸, or 2) 0-2 errors (out of 10 questions) on the Short Portable Mental Status Questionnaire. Finally, the individual must be able to provide consent to participate in the study by demonstrating understanding.

Exclusion criteria will be: 3 or more errors on the Short Portable Mental Status Questionnaire; major psychiatric disorder, neurological or autoimmune conditions affecting cognition; systemic medical illnesses; substance abuse or dependence (DSM-V criteria); and current depression (defined as Geriatric Depression Scale [GDS]¹⁹ score > 15).

Recruitment:

For both Aim 1 and 2, participants with aMCI and their study partners will be recruited directly from [name] ongoing longitudinal study (**Bio-AD**) at the Rocky Mountain Alzheimer's Disease Center. [name] will directly refer aMCI patients to our study who meet the specified criteria, who have undergone their Bio-AD assessments within the past 6 months, and who consented to be invited to other research studies. Additionally, after obtaining a Health Insurance Portability and Accountability Act (HIPAA) waiver from COMIRB, a list of potential participants (patients) will be obtained from the UHealth Seniors Clinic clinical dementia outreach program. We will ask for a list of patients who are 60 years of age or older, have their preferred language listed as English, and do not have a diagnosis of moderate or severe dementia.

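### For patients outside Bio-AD, the objective memory impairment requirement is met by 0 to 2 SPMSQ errors, the exact complement of the exclusion, so a perfect score counts as impairment

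*Protocol*

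**What the plan says.** Section IV.B of the protocol (Description of Population to be Enrolled) bases inclusion on published clinical criteria for mild cognitive impairment, narrowed to early memory impairment. The reason given is that "our goal is to enrich our aMCI cohort for likely AD pathology". Three clinical determinations apply to everyone: "a) cognitive complaint that reflects a decline in cognition; b) preservation of independence in functional activities; and c) not meeting criteria for a dementia". The protocol then adds that "objective neuropsychological impairment in one or more domains, including memory, will be based on either" of two routes. The first is classification as aMCI in the Bio-AD cohort study, which uses comprehensive neuropsychological criteria. The second reads "2) 0-2 errors (out of 10 questions) on the Short Portable Mental Status Questionnaire". Capacity to consent is also required.

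The next paragraph begins "Exclusion criteria will be: 3 or more errors on the Short Portable Mental Status Questionnaire" and goes on to psychiatric, neurological, medical, substance-use and depression exclusions.

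For patients not in Bio-AD, section IV.A (Potential Modifiers of ACP Outcomes) gives two possibilities. The team will "offer participation in Bio-AD if they agree to participate in the recruitment data base", or it will "not collect these baseline measures that are outlined in Table 6 due to the additional time requirements".

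The SAP, dated May 2018 against February 2019 for the protocol, words the impairment criterion differently. Under Supplement Aim 1 it asks for scores 1 SD below norms on two memory tests and has no SPMSQ route. Supplement Aim 2 applies the same criteria.

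**The concern.** The 0 to 2 error range limits how impaired a patient may be. It is written, however, in the place where the protocol should say how impairment is shown. A patient outside Bio-AD who answers all ten questions correctly meets the objective impairment requirement.

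Among the stated criteria for these entrants, only the cognitive complaint points towards impairment. Preserved independence, absence of dementia, capacity to consent and the other exclusions limit severity or remove competing causes. None of them shows a memory deficit.

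What is at stake is who the results describe. Question 2a asks whether aMCI dyads can be recruited and can report outcomes, and section IV.C says the data will inform pragmatic trials in aMCI. Recruitment, survey completeness, help needed with questionnaires and advance directive completion could come partly from people with a complaint but unconfirmed aMCI. The secondary analysis of memory against advance care planning outcomes is also affected, because only entrants who choose to join Bio-AD would have the Table 6 measures. For this group the analysis may be incomplete and self-selected.

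**Working it through.** The plan gives no figure to reproduce here; section IV.F states that a power calculation is not appropriate. The check is of the rule itself.

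**1. What the SPMSQ route selects (protocol IV.B).** Possible results are 0 to 10 errors, which is 11 values.
- Meets the impairment requirement: {0, 1, 2}, 3 values.
- Excluded: {3, ..., 10}, 8 values.
- In both sets: 0 values. In neither: 11 − (3 + 8) = 0 values.

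The two sets are exact complements. Among people who pass the exclusion, the share removed by the requirement is 0%. Zero errors lies in the qualifying set.

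**2. Whether another stated step supplies memory evidence (protocol IV.A, IV.B and IV.E).**
- The Seniors Clinic list comes from a dementia outreach program, but it is requested on age 60 or over, English as preferred language and no moderate or severe dementia.
- Primary care providers judge whether a patient suits a group visit.
- Flyers and web advertisements also recruit, with no memory test attached.
- More than 90% of the administrative list is expected to be eligible, so little screening out is anticipated.
- Clinic patients may have had earlier work-up: IV.E cites more than 1,200 aMCI and ADRD patients evaluated at the recruiting sites. The protocol does not require that work-up as proof.
- Table 6 testing happens only for those who join Bio-AD.

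**3. Contrast with the SAP rule.** Assume standard normal scores in a person with normal memory. The correlation r between tests is an assumption. P(Z < −1) = 0.1587. The chance of falling below the cutoff on both of two tests is:

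| r | Probability |
|---|---|
| 0 | 0.1587² = 0.025 |
| 0.5 | 0.063 |
| 1 | 0.159 |

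The SAP names three kinds of memory task in the co-investigator's screening (list learning, story recall, visual recall). If the rule were any two of three, the figures would be 0.068, 0.120 and 0.159. Under either reading, a person with normal memory passes the SAP rule at most about 16% of the time. A perfect SPMSQ scorer meets the protocol's requirement every time.

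**4. How many patients could be affected.** Planned patients: 6 (Aim 1) + 20 (Aim 2) = 26. The share entering outside Bio-AD is not stated, so 26 is a logical ceiling and not an estimate.

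**5. Recruitment room if memory evidence were required.** Section IV.B plans to approach up to 100 patients with about 25% agreeing: 100 × 0.25 = 25 patients, against 26 needed. If a fraction f of clinic patients had usable memory results (assumption), clinic approaches would rise by 1/f: 1/0.75 = 1.33, 1/0.50 = 2, 1/0.25 = 4.

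**6. Precision of results split by route.** With 20 Aim 2 patients split 10/10 (assumption), 5 of 10 has an exact (Clopper-Pearson) 95% interval of 18.7% to 81.3%. In a smaller cell, 3 of 5 has 14.7% to 94.7%.

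**The case against.** The best defence is that this is a misplaced severity limit and not an intention to treat a perfect score as impairment. The protocol states a focus on early memory impairment and describes its population as "Individuals with amnesic Mild Cognitive Impairment and study partners from UHealth settings". Bio-AD is named first as the recruitment source for both aims and had already assessed 32 aMCI patients, so entry of all 26 by the SPMSQ would run against the plan described. The pre-screening template used to determine eligibility is not in the text reviewed and could ask for more. The later protocol may also have widened entry on purpose, and the SAP is not a clean standard, since it describes Aim 2 patients as having aMCI or early ADRD. Finally, this is a small, largely qualitative feasibility study, and the protocol already discloses that Table 6 data will be missing outside Bio-AD.

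Much of this stands as a limit on size. The number of unimpaired entrants is unknown and may be small, and the probabilities in step 3 describe the SAP rule, not this cohort. None of it repairs the criterion. If the SPMSQ was meant only as a limit, the wording is wrong and should change. If entry was widened deliberately, the protocol still demands objective impairment including memory and still calls every entrant aMCI. The small sample does not answer the point either, because the question is who is studied, not power. The objection that a stricter rule would strain recruitment is fair, and step 5 shows no slack in the stated plan. It counts against one of the two options below, not against the other.

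**Conclusion.** The concern holds for the criteria as stated in the protocol, and it should be fixed. Outside Bio-AD, the objective impairment requirement selects nobody beyond the exclusion, and no other stated step requires objective memory evidence. This route does nothing to enrich for memory impairment. Bio-AD referrals are not affected.

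The conclusion about the rule is certain from the text. Its practical effect cannot be quantified from the documents: neither the share entering outside Bio-AD nor the number without impairment is known, and the direction of any bias is not established. The conclusion rests on the visible criteria; a pre-screening template that required memory evidence would reduce the practical effect but would still leave the protocol text wrong.

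**What to change.** Keep the SPMSQ only as the exclusion at 3 or more errors and remove it as evidence of impairment. Then reconcile protocol IV.B with the SAP criterion in one of two ways:

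- State what existing objective memory evidence entrants outside Bio-AD need, for example test results already in the medical record.
- If none is required, describe these entrants as having a cognitive complaint without confirmed aMCI, and limit the aMCI conclusions accordingly.

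In either case, record entry route and describe the sample by route. Tabulate recruitment, retention, survey completeness, level of assistance and advance directive completion by route. Make no tests between routes, and do not split group-level fidelity or debriefing results. The wide intervals in step 6 are the reason to keep this descriptive.

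**Cost.** Relabelling and recording route takes a wording amendment, one data field and one descriptive table, with no extra recruitment. Requiring memory evidence costs more: fewer clinic patients may qualify and clinic approaches rise by the 1/f factor in step 5. If that option is chosen, the limit of 100 approaches should be revisited at the same time.

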Existing aMCI longitudinal research cohort: [name], PhD (Co-investigator) is Principal Investigator on a prospective study of aging and cognitive decline that is successfully recruiting subjects with aMCI between the ages of 65-89 at the Rocky Mountain Alzheimer’s Disease Center: COMIRB number 15-1774, Rocky Mountain Alzheimer’s Disease Center at the University of Colorado School of Medicine (RMADC at UCSOM) Longitudinal Biomarker and Clinical Phenotyping Study). Specifically, in the “Longitudinal Biomarker and Clinical Phenotyping” study (**Bio-AD**; PI: [name]), she has comprehensively assessed 32 aMCI patients (mean age: 72 years; 52% female), with a goal of recruiting at least 75 aMCI patients over two years. All aMCI patients enrolled in Bio-AD have a study partner who attends each visit and current retention rates are over 90% for the annual in-person visits. All Bio-AD participants have consented to be contacted about future studies.

This study will leverage [name] study by inviting individuals with aMCI and study partners to participate. A key strength of this approach is that baseline measures of cognition and mood, as well as informant-based measures of everyday functioning will be completed through [name] ongoing Bio-AD study, and all data will be available for the proposed study. For example, all aMCI individuals have completed cognitive testing (i.e., Spanish and English Neuropsychological Assessment Scales [SENAS] and National Alzheimer’s Coordinating Center [NACC] measures) and mood assessment (i.e., Geriatric Depression Scale [GDS], perceived stress scale [PSS]). Study partners have completed measures of clinical severity (i.e., Clinical Dementia Rating [CDR; global severity] and NACC functional activities questionnaire [FAQ]).

There are five intervention domains that facilitate patient engagement in ACP decision making: group characteristics, facilitation approaches, ACP resources, primary care provider (PCP) integration, and clinic resources (**Table 4**). The ENACT Group Visits already incorporates reminder calls, written materials, and short videos, which we expect will promote participation in aMCI individuals.

Table 4. Intervention	Components in ENACT Intervention	Potential Adaptations Appropriate for ENACT Memory Group Visit
Group characteristics	Age; Gender; Group size	Smaller group sizes (up to 4 dyads, 8 total participants)

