Upon completion of the administrative data pulls, Seniors Clinic primary care providers will be sent a letter/e-mail informing them about the study. We will ask them to review a list of their patients and to refer patient(s) who would be appropriate for the study based on their judgment that the patient is appropriate for a group visit (i.e. does not have severe cognitive impairment or hearing loss to make a group visit very difficult). Clinicians will be asked to provide

permission for the study team to contact their patients by letter to describe the research study and offer patients the opportunity to decline to be contacted by study staff. We will obtain permission from all of the Service Chief(s) before their clinicians are contacted.

We will specifically recruit both men and women, ages 60 and older, and purposefully invite individuals from diverse self-reported racial/ethnic backgrounds to maximize potential for generalizability. Patients will be contacted by study personnel by letter (or up to 2 emails through MyHealth Connection, if that is their preferred contact method) and/or up to 3 phone call attempts.

[figure not shown]
We will also recruit patients directly from clinic by posting flyers in approved areas in the clinics and utilizing University of Colorado's free web-based advertisements. Participants can contact study staff in person, by phone, or by email.

We expect that >90% of patients from the administrative data pull will be eligible based on study criteria. Prior to arranging for a study consent visit, we will determine eligibility using the pre-screening consent template. Based on our preliminary experiences, around 25% will agree to participate and provide informed consent. To reach a goal of 52 enrolled participants (including patients and study partners), we anticipate approaching up to 100 patients (and their associated study partner). We will slightly over-enroll the longitudinal focus group (recruiting 12 total participants) because we expect that some participants may not participate in all three focus groups over the one year study period. We will monitor recruitment and retention to understand reasons for declining. Additionally, we will recruit five patient-study partner dyads (10 participants) per ENACT Memory Group Visit n-of-1 prototype because we have had an at least 20% cancellation or no-show rate in our prior experience.

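### Does approaching up to 100 patients at about 25% agreement fall short of the 52 participants the Protocol plans to enrol?

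*Protocol*

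**What the plan says.** Protocol Section IV.B (Population and Setting) sets six patients and six study partners for Aim 1. For Aim 2 it says "Aim 2 will recruit 20 older adults", with the same number of partners. The Recruitment text that follows gives three planning figures:

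- Eligibility: "We expect that >90% of patients from the administrative data pull will be eligible based on study criteria".
- Agreement: "around 25% will agree to participate and provide informed consent", attributed to the team's preliminary experience.
- Contacts: "To reach a goal of 52 enrolled participants (including patients and study partners), we anticipate approaching up to 100 patients", each with a study partner.

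Between the first two it places the eligibility check: "Prior to arranging for a study consent visit, we will determine eligibility using the pre-screening consent template". Five dyads are recruited per group visit "because we have had an at least 20% cancellation or no-show rate in our prior experience".

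The administrative list is not the only source. The lead of the Bio-AD cohort "will directly refer aMCI patients to our study who meet the specified criteria", and flyers and web notices invite people to contact the staff themselves. Section IV.E names further recruitment routes in case of slow accrual. Section IV.F declines a power calculation. The SAP gives neither an agreement rate nor a number to approach.

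**The concern.** A reader who multiplies the stated figures does not get 52. A quarter of 100 is 25 dyads, not 26. The order of the text (eligibility, pre-screening, then agreement) also suggests that the quarter may apply only to those who pass screening, which lowers the yield further.

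Recruitment feasibility is one of the study's own questions (Question 2a). If the planned rate has no defined denominator, the observed rate cannot be set cleanly against it, and a later trial would inherit the ambiguity. Any enrolment shortfall would also use up part of the allowance for no-shows that is built into five dyads per group.

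**Working it through.** **Inputs.** All are from Protocol Section IV.B unless noted: 6 dyads (Aim 1); 20 dyads (Aim 2); up to 100 patients approached; about 25% agreeing; more than 90% eligible, for the administrative list only; at least 20% no-show; 32 Bio-AD patients assessed so far (Section III).

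**The goal.** 6 + 20 = 26 dyads, and 26 × 2 = 52 people. The no-show allowance also reproduces: 4 / (1 − 0.20) = 5 dyads per group, and 16 / 0.80 = 20 in all.

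**Yield if 25% is of those approached.** 100 × 0.25 = 25 dyads = 50 people. The gap is 1 dyad. The agreement rate that gives exactly 26 dyads is 26 / 100 = 26%. The number to approach at exactly 25% is 26 / 0.25 = 104.

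**Yield if 25% is of those eligible.**

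| Eligible share applied to all 100 | Dyads | People | Approaches needed for 26 dyads |
|---|---|---|---|
| 90% (floor of the stated range) | 100 × 0.90 × 0.25 = 22.5 | 45 | 26 / 0.225 = 115.6, so 116 |
| 95% (assumed, for illustration) | 100 × 0.95 × 0.25 = 23.75 | 47.5 | 26 / 0.2375 = 109.5, so 110 |
| 100% | 25 | 50 | 104 |

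At 90% eligible, the break-even agreement rate is 26 / 90 = 28.9%.

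**Sensitivity to the other sources.** Suppose (assumption) that the 32 Bio-AD patients are all among the 100 and none is lost to ineligibility.

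- At 25% agreement throughout, and 90% eligibility in the other 68: 32 × 0.25 + 68 × 0.225 = 23.3 dyads.
- The Protocol gives no agreement rate for Bio-AD patients. If the other 68 yield 25%, then 26 dyads need (26 − 17) / 32 = 28.1% agreement in Bio-AD.
- If the other 68 yield 22.5%, they need (26 − 15.3) / 32 = 33.4%.

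The documents exclude neither value. Flyer and web respondents, who need not count among the 100, add a yield that none of these sums includes.

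**Chance of reaching the goal.** If the rates were exact and patients independent, the binomial chance of at least 26 dyads from 100 would be 0.233 at 22.5%, 0.447 at 25% and 0.538 at 26%. A figure set near the expected yield always gives a chance near one half, so this does not point to an error.

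**The case for a change.** The best case for a change is the missing denominator, which is real whichever reading is right. At the stated rates, neither base gives 26 dyads from the 100 contacts. Since 100 is a ceiling, approaching fewer would widen the gap.

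It can also be said that 45 to 50 enrolled people should not be compared with the planned lower end of 12 + 32 = 44, because 32 is what remains of 40 after 20% no-shows. If Aim 1 is filled first and no-show is 20% (both assumptions), Aim 2 attendance would be (25 − 6) × 0.8 = 15.2 dyads, about 30 people. On the lower yield it would be (22.5 − 6) × 0.8 = 13.2 dyads, about 26 people. Both are below 32. Finally, the clinics named as fallbacks in Section IV.E overlap with the setting already listed in Section IV.B.

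Part of this stands. The base is unstated, and the like-for-like comparison with 44 is fair criticism. But the lower attendance figure depends on the 22.5-dyad yield, which the Protocol's own figures do not support. The eligibility rate is a lower bound, it belongs to the administrative list, and clinicians review that list before anyone is contacted. Bio-AD referrals already meet the criteria. On the approached base, attendance is 15.2 dyads against 16, a difference of less than one dyad across four groups. Nothing in the analysis depends on that difference. The overlap of clinics weakens the fallback but does not remove it, since Section IV.E also names a recruitment specialist.

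**Conclusion.** No change follows. On the direct reading, the contact estimate misses the goal by one dyad in 26, and a rate of 26% in place of 25% removes the gap. The agreement rate, the number of contacts and the eligibility rate are all given as approximations or bounds, so a difference of that size is rounding. The larger shortfall of 3.5 dyads needs two extra steps: exactly 90% eligibility, and that rate applied to every source.

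The missing base is a gap of detail. Section IV.F already tracks recruitment and participation rates with reasons for not taking part. An analyst would report the numbers approached, eligible and consented, which gives the rate on either base. The plan sets no pass mark and no formal comparison with 25%.

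Raising the contact figure from 100 to somewhere between 104 and 116 would alter no target, analysis or conclusion. A larger number chosen for high assurance of 26 dyads would import a standard that this feasibility study does not set. The conclusion rests on reading the 100 as a planning estimate, which the Protocol's tentative wording supports.
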